The duration of solicited AEs of any grade (see Section 6.2.1.9) will be summarized. The start date is the first day during the 7-day solicitation period with the symptom at grade > 0 while the stop date is the last day with the symptom at grade > 0 in or beyond the solicited period. In addition, the duration for specific grade(s) for each symptom defined as the number of days in the reporting period with grade above or equal to specific grade will be summarized.

Prolonged solicited AEs that continue beyond Day 7 or Day 28 will be identified using a flag in listing of AEs.

The number of completed eDiary days in the solicited period for a participant will be summarized by study group using frequency table.

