6.2.1.9. Duration of Events

The duration of an event with a start and end date will be the difference between the start and end date plus 1 day, i.e., an event that starts on 03MAR2018 and ends on 12MAR2018 has a duration of 10 days.

For any grade, duration of solicited AE is defined as Start date – Stop date + 1, with Start date defined as the first day with the symptom at Grade ≥ 0 within the 7-day solicitation period and Stop date defined as the last day with the symptom (i.e., Grade > 0) in or beyond the solicited period. For solicited AE continuing beyond Day 28, stop date will be assigned the end of study.

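### SAP 6.2.1.9 gives every solicited event that continues past Day 28 an end-of-study stop date, even if it resolved on a recorded earlier day

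*SAP*

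**What the plan says.** SAP 6.2.1.9 opens with a general convention, end minus start plus one, and a worked example: "an event that starts on 03MAR2018 and ends on 12MAR2018 has a duration of 10 days". For solicited events of any grade it then gives:

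- the formula: "duration of solicited AE is defined as Start date – Stop date + 1";
- the start: "the first day with the symptom at Grade ≥ 0 within the 7-day solicitation period";
- the stop: "Stop date defined as the last day with the symptom (i.e., Grade > 0) in or beyond the solicited period";
- a final rule: "For solicited AE continuing beyond Day 28, stop date will be assigned the end of study".

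SAP 4.2.1.1 plans the duration summary and gives the same stop date with no end-of-study substitution: "the stop date is the last day with the symptom at grade > 0 in or beyond the solicited period". It starts the event at the first day in the 7-day period with a grade above zero. Its grade-specific durations are a different quantity, "the number of days in the reporting period with grade above or equal to specific grade". It also provides that "Prolonged solicited AEs that continue beyond Day 7 or Day 28 will be identified using a flag in listing of AEs".

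On follow-up, daily eDiary recording of ongoing solicited events stops at Day 28 (SAP 4.2.1.1; protocol 10.3.5.2) and the device goes back at Day 29 (protocol 10.3.5.1). The same sections have these events followed until they resolve or another listed end point is reached. Protocol 10.3.5.6 has non-serious adverse events followed to Day 183.

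**The concern.** The Day 28 sentence overrides the sentence before it and disagrees with SAP 4.2.1.1. An event that ended on Day 29 or Day 35, with that date on record, has one duration under 4.2.1.1 and a far longer one under 6.2.1.9. A programmer has to choose, and the more specific text points to the wrong answer.

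At stake is a planned safety description. SAP 4.1.1 summarises continuous data with the mean, SD, median, interquartile range, minimum and maximum. A reaction that lasted about four weeks would appear as one of about six months, which would mislead a reader looking at the maximum or mean for that symptom and group.

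**Working it through.** **Inputs**

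- Convention and example: SAP 6.2.1.9, 3 to 12 March 2018 lasts 10 days.
- Participant-level end of study: Day 183 (protocol 10.3.5.6).
- Last-visit window: 180 to 210 days after Visit 1 (protocol Table 4; SAP Table 10), which is study Days 181 to 211.
- Group size: 120 in Phase 2 (SAP 1.2).
- The number in a group reporting a given symptom, n, is not in the documents. I assume 30, 60 and 90.

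**Step 1: the plan's own example.** Stop − Start + 1 = 12 − 3 + 1 = 10 days, as stated. The solicited-event formula as printed gives 3 − 12 + 1 = −8. The printed order is therefore a slip, and I use Stop − Start + 1.

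**Step 2: one event under each rule (end of study = Day 183)**

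| Symptomatic days | Last symptomatic day as stop | Literal Day 28 rule |
|---|---|---|
| 1 to 28 | 28 | 28 |
| 1 to 29 | 29 | 183 − 1 + 1 = 183 |
| 7 to 29 | 29 − 7 + 1 = 23 | 183 − 7 + 1 = 177 |
| 1 to 60 | 60 | 183 |

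One extra symptomatic day takes the value from 28 to 183. Across the visit window, the Days 1 to 29 event becomes 181 to 211 days.

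**Step 3: the excess.** It equals the assigned end-of-study day minus the true last day. With Day 183 it is 183 − 29 = 154 for an event ending on Day 29 (152 to 182 across the window), 183 − 100 = 83 for one ending on Day 100, and 0 for one still present at Day 183.

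**Step 4: effect on the summary.** One event ending on Day 29 shifts the group mean by 154/n. For illustration, I assume the other n − 1 durations cycle through 1, 2 and 3 days. For n = 30 those 29 values sum to 57, so the mean is (57 + 29)/30 = 2.87 with the true stop date and (57 + 183)/30 = 8.00 under the literal rule. SDs use the n − 1 denominator.

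| n | Mean, true | Mean, literal | Shift 154/n | SD, true | SD, literal |
|---|---|---|---|---|---|
| 30 | 2.87 | 8.00 | 5.13 | 5.00 | 33.06 |
| 60 | 2.43 | 5.00 | 2.57 | 3.58 | 23.38 |
| 90 | 2.29 | 4.00 | 1.71 | 2.96 | 19.10 |

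The maximum goes from 29 to 183 in each case. The median stays at 2 and the quartiles at 1 and 3.

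**The case against.** The best defence is that the Day 28 sentence is a censoring rule. Daily capture ends at Day 28, so an event continuing past it can be read as one still open when recording stops, and end of study is then a reasonable date. That may well be what the authors meant, but the sentence does not say so. Follow-up continues after Day 28, and for adverse events with no stop date at all SAP 6.2.2.1 already uses a different date, the last contact.

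Three further points stand as limits on size:

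- The 154-day excess is the largest on the Day 183 reading. Later resolution makes it smaller, and nothing in the documents shows that any such event is expected. Protocol 2.3 expects reactions to resolve within a few days.
- The documents do not name the field that would hold a stop date after Day 28, so whether a real date would be discarded depends on data specifications not seen here.
- End of study is not defined in the sentence. Protocol 4.4 defines it for the whole trial, as late as 8 months after the last participant's last visit. On that reading the assigned durations would be longer still: for the last participant, with 8 months taken as 243 days, about 183 + 243 = 426 days.

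The two drafting slips do little harm by themselves. The worked example and SAP 4.2.1.1 make the intent clear, and negative durations would be noticed at once.

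**Conclusion.** The concern holds, as a minor one. As written, the rule gives a wrong duration for any solicited event that resolved on a recorded day between Day 29 and the end of study. For an event on Days 1 to 29 the value is 183 days instead of 29, taking end of study as the participant's Day 183. The changes in mean and SD rest on assumed counts and durations. If no event passes Day 28, the effect is zero.

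The damage is confined to the mean, SD and maximum of the any-grade duration summary. The median and interquartile range are little affected. The co-primary percentages, grade tables, holding rules and grade-specific durations do not use this derivation.

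**What to change.** Rewrite the paragraph in SAP 6.2.1.9 so that:

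- duration is Stop − Start + 1;
- the start is the first day in Days 1 to 7 with a grade above zero, matching SAP 4.2.1.1;
- the stop is the recorded last symptomatic day, including a day after Day 28;
- only for events that are unresolved or have no recorded stop date, the stop is the participant's last contact date, in line with SAP 6.2.2.1.

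Using last contact also removes the doubt over what end of study means. For completers it is normally the Day 183 visit or contact, so it changes the result mainly for early withdrawals. State with each summary how many durations are censored; the Day 28 flag already planned for the listing helps to find them.

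The cost is one sentence, two typographical corrections and one derivation, with no new visits or data collection. The data specifications need checking for where a stop date after Day 28 is stored; where none was recorded, the last-contact rule applies.

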6.2.1.10. Counting Rules for Occurrences of Solicited and unsolicited Events

When the occurrences of solicited events are summarized, each event recorded as having occurred during a specific period will be counted as only 1 occurrence regardless of the number of days on which it occurs.

Accordingly for the summary presenting the number and percentage of participants reporting any solicited and unsolicited adverse events excluding SAE, a solicited AE starting within the solicited period (day 1-7) will be counted as one event while unsolicited AE, excluding prolonged solicited AE will be counted as different event when these are associated to different MedDRA Primary Term or different start date. For instance, a participant with fatigue for several days within the solicited period, with fatigue prolonged beyond the solicited period and with fatigue restarting later in the unsolicited period will contribute as 2 occurrence of fatigue.

6.2.1.11. AESIs

GSK MedDRA queries will be used to identify AESI:

- pIMD: refer to Table 15 from the protocol
- Severe hypersensitivity (including anaphylaxis): Grade 3 unsolicited AEs under MedDRA SMQ hypersensitivity, narrow search (includes anaphylaxis), with an onset within 24 hours after dosing

Myocarditis/pericarditis. In addition to identification based on the medical and scientific judgement of the investigator, the following non-exhaustive list of PTs will be used: autoimmune myocarditis; eosinophilic myocarditis; giant cell myocarditis; hypersensitivity myocarditis; immune-mediated myocarditis; myocarditis; autoimmune pericarditis, pericarditis; pericarditis adhesive; pericarditis constrictive; pleuropericarditis.

These pIMD, myocarditis and pericarditis queries may be revised based on MedDRA dictionary version.

AESI summaries will include AEs identified by either the investigator or the MedDRA queries.

6.2.2. Handling of Partial Dates

6.2.2.1. Dates

When partially completed dates (i.e., dates missing a day and/or month) are used in calculations, the following standard rules will be applied:

- A missing day will be replaced by 15
- A missing day and month will be replaced by June 30th.
- For stop date, the maximum between the start and imputed stop date by above rule will be used instead.

The following exceptions apply:

- Adverse events start dates with missing day:
 - If the event starts in the same month as the study dose administration then the contents of AE.AESTRTPT (the flag indicating if the event occurred before or after study dose) will be used to complete the date. If ‘after study dose’ is selected, the imputed start date will match the study dose given during that month. If ‘before study dose’ is selected, the imputed date will be one day before the study dose given during that month.
- Adverse events start dates with missing day and month:
 - If the event starts in the same year as the study doses, the contents of AE.AESTRTPT (the flag indicating if the event occurred before or after study dose) will be used to complete the date. If ‘after study dose’ is selected, the imputed start date will match the study dose given during that year. If ‘before study dose’ is selected, the imputed date will be one day before the study dose given during that year.
- Adverse events stop dates with missing day: the last day of the month or the last contact date will be used, which ever come first.
- Adverse events stop dates with missing day and month: the last day of December or the last contact date will be used, which ever come first.
- Adverse events stop dates with missing day, month, and year: the last contact date will be used.

All other cases of incomplete AE or concomitant medication/vaccination start date will follow the standard rules above.

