### 5.2.2. Prior/Concomitant therapy

11. Administration of an influenza vaccine (including any of the study investigational vaccines) within 180 days before enrollment or planned administration within 28 days (Day 29) after the study intervention administration.
12. **Phase 1:** Administration of a vaccine not foreseen by the study protocol in the period starting 28 days (Day -28) before the study intervention administration, or planned administration within 28 days (Day 29) after the study intervention administration\*.  
**Phase 2: Administration of a vaccine not foreseen by the study protocol in the period starting 15 days (Day -15) before the study intervention administration, or planned administration within 28 days (Day 29) after the study intervention administration\*.**  
*\*In case emergency mass vaccination for an unforeseen public health threat (e.g., a pandemic) is recommended and/or organized by public health authorities outside the routine immunization program, the time period described above can be reduced to 7 days if, necessary for that vaccine, provided it is used according to the local governmental recommendations and that the Sponsor is notified accordingly.*
13. Use of any investigational or non-registered product (drug, vaccine or invasive medical device) other than the study intervention during the period beginning 30 days before the study intervention administration, or their planned use during the study period.
14. Administration of long-acting immune-modifying drugs within 90 days before enrollment or planned use at any time during the study period (e.g., infliximab).
15. Administration of immunoglobulins and/or any blood products or plasma derivatives during the period starting 90 days before the study intervention administration, or planned administration during the study period. Administration of monoclonal antibodies specifically directed against the spike protein of Severe Acute Respiratory Syndrome Coronavirus 2 (SARS-CoV-2), for treatment of COVID-19 disease is allowed.
16. Chronic administration (defined as more than 14 days in total) of immunosuppressants or other immune-modifying drugs during the period starting 3 months prior to the study intervention administration. For corticosteroids, this will mean prednisone equivalent  $\geq 20$  mg/day. Inhaled, topical and intraarticular steroids are allowed.

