6.1.4. Protocol Deviations

Important protocol deviations are a subset of protocol deviations (PDs) that may significantly impact the completeness, accuracy, or reliability of the study data or that may significantly affect a participant's rights, safety, or well-being. Important PD rules will be developed and finalized before database lock.

Important PDs include, but are not limited to, the following:

All participant data is excluded from the PPS:

- Study intervention not administered at all
- Invalid/missing informed consent
- Fraudulent data
- Participants got dosed but not as per protocol
- Study intervention storage temperature deviation which is not accepted by quality
- Expired study intervention administered

- Ineligible participant
- Participants randomized using the wrong stratification factor (incorrect age group)

Participant data collected on the day or after the event is excluded from the PPS:

- Influenza disease infection, new malignancy and immunocompromised condition
- Administration of concomitant vaccine(s) forbidden in the protocol
- Administration of any medication forbidden by the protocol, namely administration during the study period of investigational or non-registered product (drug, vaccine or invasive medical device) other than the study intervention, of long-acting immune-modifying drugs or of immunoglobulins and/or any blood products or plasma derivatives with the exception of monoclonal antibodies specifically directed against the spike protein of SARS-CoV-2 virus, for treatment of COVID-19 disease.

Participant lab data collected on the day of the event is excluded from the PPS:

- Participants did not comply with blood sample schedule (see [Table 9](#) and [Table 10](#))
- **CCI** [REDACTED]
- Serological results available but results unreliable (e.g., wrong blood sample management)

The number of participants with important protocol deviations will be summarized by study group across time points and at Day 28 and Day 183. Important protocol deviations will be listed with date of occurrence, deviation description, and analysis set from which participant is excluded. Important protocol deviation summary will be based on the Enrolled Set.

The important PDs will be reported in the Clinical Study Report (CSR). The important PDs leading to elimination from the PPS will be summarized for the ES and the important PDs leading to elimination from the ES will be summarized for the Enrolled Set.

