6.1.5. Prior and Concomitant Medications

Concomitant medications are defined as any medications and vaccines (other than study intervention) taken after the study intervention administration. Any medication or vaccine (other than study intervention) started prior to the study intervention administration and continued after the study intervention administration will be considered a concomitant medication.

Concomitant medications/vaccinations will be coded using both the GSK Drug and WHO Drug dictionaries and will be listed and summarized descriptively (any medication, any antipyretic, and any antipyretic taken prophylactically, respectively) by study group using the ES.

The antipyretic classification is derived from the following ATC code:

ATC Code
A03D, A03DA, A03DB, A03DC, A03EA
M01, M01A, M01AA, M01AC, M01AE, M01AG, M01AB, M01AH, M01AX, M03B, M03BA, M03BB, M03BB, M03BC, M03BX
N02BG, N02AC, N02AG, N02AX, N02B, N02BA, N02BB, N02BE
R05, R05D, R05X

The percentage of participants using concomitant medication (any medication, any antipyretic and any antipyretic taken prophylactically, respectively) during the 28-day follow up period (i.e., Day 1 - Day 28 post-dosing) will be summarized by group.

This antipyretic list may be revised based on WHO dictionary version.

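### Incomplete start dates of concomitant drugs and vaccines are imputed to the 15th or 30 June without reference to the dose or the Day 29 draw, although adverse event start dates are protected

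*SAP*

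**What the plan says.** SAP 6.2.2.1 has two fixed rules for partial dates used in calculations: "A missing day will be replaced by 15" and "A missing day and month will be replaced by June 30th". For adverse event starts in the month or year of dosing it departs from them: "then the contents of AE.AESTRTPT (the flag indicating if the event occurred before or after study dose) will be used to complete the date". Concomitant products get no such exception: "All other cases of incomplete AE or concomitant medication/vaccination start date will follow the standard rules above". Partial stop dates of these products have one safeguard, which refers to the start date and not to the dose: "For stop date, the maximum between the start and imputed stop date by above rule will be used instead".

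The dates are used in these places:

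- SAP 6.2.1.7 derives the onset day of a concomitant medication or vaccination from its start date relative to the dose.
- SAP 6.1.5 tabulates medication and antipyretic use over Day 1-28, with this definition: "Concomitant medications are defined as any medications and vaccines (other than study intervention) taken after the study intervention administration". A product started earlier and continued past the dose also counts.
- SAP section 3 requires, for the PPS, no prohibited medication or vaccination before Day 29. For forbidden vaccines and drugs, SAP 6.1.4 adds: "Participant data collected on the day or after the event is excluded from the PPS". The detailed deviation rules are still to be finalized before database lock.

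**The concern.** The SAP recognises that a fixed date can reverse the order of an event and the dose, and repairs this for adverse events only. For concomitant products the imputed order depends on the calendar day of dosing, not on what happened. The direct consequence is misdated onset days and misplaced records in the Day 1-28 tables. There is a possible second consequence, because the PPS carries the primary immunogenicity analyses (Protocol 9.3) and its rules turn on whether a forbidden product came before the Day 29 sample. If the same imputed dates were used there, a valid Day 29 result could be dropped or a compromised one kept.

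**Working it through.** **The plan's own PPS-dependent figure.** SAP 5.2 gives a 1.36-fold half-width for the geometric mean ratio, with 108 evaluable per group and SD 0.5 on the log10 scale. 10^(1.96 × 0.5 × √(2/108)) = 1.359, so it reproduces.

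**1. Post-dose product, month-only start, in the dosing month.** Let dose day d and start day s ≥ d be uniform over a 30-day month.

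- Possible pairs: 30 + 29 + … + 1 = 465.
- The 15th precedes the dose when d is 16 to 30: 15 + 14 + … + 1 = 120 pairs.
- Share imputed before the dose: 120/465 = 25.8%. For d > 15 the share is 100%.

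Example: dose 20 September, drug 25 to 27 September, both dates recorded only as September. The start becomes 15 September, and the stop becomes the later of 15 and 15 September. The record ends before the dose and leaves the Day 1-28 table. If the stop of 27 September is known, the carry-over rule in SAP 6.1.5 keeps it.

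**2. Day 1-28 tables over a wider window.** Assumptions not in the documents: doses uniform over September to November 2023, true starts uniform from 28 days before to 56 days after dose, courses of 1 to 7 days. Counting every day combination:

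| Missing | Records misplaced (in or out) |
|---|---|
| Start day only | 10.5% to 13.2% |
| Start and stop day | 18.0% |

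**3. Year-only start.** Phase 2 doses were set by the amendment of 28 August 2023, so dosing is taken to be later. From 30 June to 29 August 2023 is 60 days. A year-only 2023 start is thus placed at least 60 days before every Phase 2 dose, even if the product was given after it.

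**4. Day 29 draw, if imputed dates were used for the PPS.** Let vaccine day v and draw day b be uniform over the same 30-day month. A result is excluded when b is on or after the vaccine date.

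- Wrongly dropped (b ≥ 15, v > b): 15 + 14 + … + 0 = 120.
- Wrongly kept (b ≤ 14, v ≤ b): 1 + 2 + … + 14 = 105.
- Wrong side: 225/900 = 25%.

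With the window and dose dates of step 2 and the draw 28 days after dose, 9.1% fall on the wrong side of the draw and 8.9% on the wrong side of the dose. Dosing in September only, or in October to December, gives 9.4% or 9.0% at the draw.

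Examples in each direction:

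- Dose 12 September, draw 10 October, vaccine 3 October recorded as October: imputed 15 October, result wrongly kept.
- Dose 20 September, draw 18 October, vaccine 25 October recorded as October: imputed 15 October, result wrongly dropped.

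**5. Scale.** The number of partial dates is not given. If 0.5% to 5% of 120 participants per group had a month-only vaccine date (assumed), that is 0.6 to 6 people. At 9.1%, 0.05 to 0.55 per group would be on the wrong side of the draw. Losing one participant from one arm moves the half-width from 1.359 to 10^(1.96 × 0.5 × √(1/107 + 1/108)) = 1.360.

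**The case against.** A reader might infer that the SAP makes PPS membership depend on imputed dates. It does not say so. The imputation rules apply when partial dates enter calculations, whereas PPS exclusions run through protocol deviations whose rules are still to be finalized (SAP 6.1.4). Nothing rules out the use of imputed dates either, so the PPS consequence is conditional.

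A reader might also infer that someone with a year-only 2023 influenza vaccination would be found ineligible and lose all PPS data. The criterion is "Administration of an influenza vaccine (including any of the study investigational vaccines) within 180 days before enrollment", and 30 June 2023 plus 180 days is 27 December 2023, so the imputed date would often fall inside the window. But eligibility is judged at Visit 1 with a two-year influenza vaccination history taken, and no text has a program recompute it from an imputed date. That inference fails.

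Other points carry weight:

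- Sites ask about medications and vaccinations at every visit and contact and must record start and end dates (Protocol 6.9). They also need to know whether a seasonal influenza vaccine was given after Day 29 to decide on later visits and samples. Partial dates should be few and their order often known. This limits the size of the problem, but SAP 6.2.2.1 does not use that knowledge.
- The 25% holds only when vaccine and draw share a month; a vaccine from the previous month is still imputed before the draw. It must not be applied to all partial dates.
- The 26% is not a table error rate. The carry-over rule rescues products with a known post-dose stop, and the tables count participants, so a second qualifying record hides a lost one.
- The study tests no hypothesis, and interim analyses use the Exposed Set (SAP 4.7), so PPS effects would not reach them.
- The documents show a before/after-dose flag for adverse events only, so it cannot simply be copied across.

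**Conclusion.** The point holds as a minor defect in a stated rule. Followed literally, SAP 6.2.2.1 can place a post-dose drug or vaccine before the dose, and the loss from the Day 1-28 tables is greatest when the stop date is partial too. The effect on the PPS depends on an assumption that the SAP neither makes nor excludes. The percentages rest on uniform dates and, for the wider window, on assumed Phase 2 dosing months. The number of participants affected is unknown and probably very small, and confidence interval precision is practically unchanged. The reason to act is that order relative to the dose and the draw should follow the record and be fixed in advance.

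**What to change.** In SAP 6.2.2.1, add an exception for concomitant medication and vaccination start dates, in the manner of the adverse event one:

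- When a product is known to have started after the dose, the imputed start is no earlier than the dose date. When it is known to have started before, it is imputed before the dose.
- The imputed start is no later than the visit or contact at which the product was first reported. Where an earlier contact, including the Day 29 visit, documents that it had not yet been taken, the imputed start falls after that contact.

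In SAP 6.1.4, state that PPS exclusions and eligibility deviations are never derived from an imputed date alone. They rest on the documented order of product, dose and draw, and unresolved cases are decided before database lock by staff blinded to assignment.

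Where the order is known, wrong-side placement at the dose and the draw falls to zero by construction. The cost is a few lines of text and some programming, a check that the database holds the visit or contact of first report, and brief review of the few unresolved cases. No new data collection from participants is needed.
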